### **DEFINITION OF SAE**

If an event is not an AE per definition above, then it cannot be an SAE even if serious conditions are met.

## SERIOUS ADVERSE EVENTS

Serious Adverse Event (SAE) is defined as any untoward medical occurrence that, at any dose:
Results in death
Is life-threatening (defined as an event in which the participant was at risk of death at the time of the event; it does not refer to an event which hypothetically might have caused death if it were more severe)
Requires inpatient hospitalization or causes prolongation of existing hospitalization (see NOTE below)
NOTE: The following hospitalizations are not considered SAEs in BMS clinical studies:

• a visit to the emergency room or other hospital department < 24 hours, that does not result in admission (unless considered an important medical or life-threatening event)

• elective surgery, planned prior to signing consent

• admissions as per protocol for a planned medical/surgical procedure

• routine health assessment requiring admission for baseline/trending of health status (eg, routine colonoscopy)

• medical/surgical admission other than to remedy ill health and planned prior to entry into the study. Appropriate documentation is required in these cases

• admission encountered for another life circumstance that carries no bearing on health status and requires no medical/surgical intervention (eg, lack of housing, economic inadequacy, caregiver respite, family circumstances, administrative reason)

• admission for administration of anticancer therapy in the absence of any other SAEs (applies to oncology protocols)

Results in persistent or significant disability/incapacity
Is a congenital anomaly/birth defect

Pregnancy and potential drug induced liver injury (DILI) must follow the same transmission timing and processes to BMS as used for SAEs (see [Section 9.2.5](#) for reporting pregnancies).

Any component of a study endpoint that is considered related to study therapy should be reported as SAE (eg, death is an endpoint, if death occurred due to anaphylaxis, anaphylaxis must be reported).

## EVALUATING AES AND SAEs

Assessment of Causality

• The investigator is obligated to assess the relationship between study intervention and each occurrence of each AE/SAE.

- A “reasonable possibility” of a relationship conveys that there are facts, evidence, and/or arguments to suggest a causal relationship, rather than a relationship cannot be ruled out.
- The investigator will use clinical judgment to determine the relationship.
- Alternative causes, such as underlying disease(s), concomitant therapy, and other risk factors, as well as the temporal relationship of the event to study intervention administration will be considered and investigated.
- The investigator will also consult the Investigator’s Brochure (IB) and/or Product Information, for marketed products, in his/her assessment.
- For each AE/SAE, the investigator must document in the medical notes that he/she has reviewed the AE/SAE and has provided an assessment of causality.
- There may be situations in which an SAE has occurred and the investigator has minimal information to include in the initial report to Sponsor. However, it is very important that the investigator always make an assessment of causality for every event before the initial transmission of the SAE data to Sponsor.
- The investigator may change his/her opinion of causality in light of follow-up information and send a SAE follow-up report with the updated causality assessment.
- The causality assessment is one of the criteria used when determining regulatory reporting requirements.

#### **Follow-up of AEs and SAEs**

If only limited information is initially available, follow-up reports are required. (Note: Follow-up SAE reports must include the same investigator term(s) initially reported.)

If an ongoing SAE changes in its intensity or relationship to study treatment or if new information becomes available, the SAE report must be updated and submitted within 24 hours to BMS (or designee) using the same procedure used for transmitting the initial SAE report.

All SAEs must be followed to resolution or stabilization.

## REPORTING OF SAES TO SPONSOR OR DESIGNEE

- SAEs, whether related or not related to study treatment, and pregnancies must be reported to BMS (or designee) immediately within 24 hours of awareness of the event.
- SAEs must be recorded on the SAE Report Form.
  - The required method for SAE data reporting is through the eCRF.
  - The paper SAE Report Form is only intended as a back-up option when the electronic data capture (EDC) system is unavailable/not functioning for transmission of the eCRF to BMS (or designee).
    - ◆ In this case, the paper form is transmitted via email or confirmed facsimile (fax) transmission
    - ◆ When paper forms are used, the original paper forms are to remain on site
- Pregnancies must be recorded on a paper Pregnancy Surveillance Form and transmitted via email or confirmed facsimile (fax) transmission

**SAE Email Address:** Refer to Contact Information list.

**SAE Facsimile Number:** Refer to Contact Information list.

**SAE Telephone Contact** (required for SAE and pregnancy reporting): Refer to Contact Information list

## **APPENDIX 4      WOMEN OF CHILDBEARING POTENTIAL DEFINITIONS AND METHODS OF CONTRACEPTION**

### **DEFINITIONS**

#### **Woman of Childbearing Potential (WOCBP)**

A woman is considered fertile following menarche and until becoming post-menopausal unless permanently sterile. Permanent sterilization methods include hysterectomy, bilateral salpingectomy, and bilateral oophorectomy.

#### **Women in the following categories are not considered WOCBP**

- Premenarchal
- Premenopausal female with 1 of the following:
  - Documented hysterectomy
  - Documented bilateral salpingectomy
  - Documented bilateral oophorectomy

Note: Documentation can come from the site personnel's review of the participant's medical records, medical examination, or medical history interview.

- Postmenopausal female
  - A postmenopausal state is defined as 12 months of amenorrhea in a woman over age 45 years in the absence of other biological or physiological causes. In addition, females under the age of 55 years must have a serum follicle stimulating hormone, (FSH) level > 40 mIU/mL to confirm menopause.

### **CONTRACEPTION GUIDANCE FOR FEMALE PARTICIPANTS OF CHILD BEARING POTENTIAL**

One of the highly effective methods of contraception listed below is required during study duration and until the end of relevant systemic exposure, defined as 5 months after the end of study treatment.\*

#### **Highly Effective Contraceptive Methods That Are User Dependent**

*Failure rate of <1% per year when used consistently and correctly.a*

- Combined (estrogen- and progestogen-containing) hormonal contraception associated with inhibition of ovulationb
  - oral
  - intravaginal
  - transdermal
- Progestogen-only hormonal contraception associated with inhibition of ovulationb
  - oral
  - injectable

### Highly Effective Methods That Are User Independent

- Implantable progestogen-only hormonal contraception associated with inhibition of ovulationb
- Intrauterine hormone-releasing system (IUS)c
- Intrauterine device (IUD)c
- Bilateral tubal occlusion
- Vasectomized partner

*A vasectomized partner is a highly effective contraception method provided that the partner is the sole male sexual partner of the WOCBP and the absence of sperm has been confirmed. If not, an additional highly effective method of contraception should be used.*

- Sexual abstinence

*Sexual abstinence is considered a highly effective method only if defined as refraining from heterosexual intercourse during the entire period of risk associated with the study drug. The reliability of sexual abstinence needs to be evaluated in relation to the duration of the study and the preferred and usual lifestyle of the participant.*

- It is not necessary to use any other method of contraception when complete abstinence is elected.
- WOCBP participants who choose complete abstinence must continue to have pregnancy tests, as specified in [Section 2](#).
- Acceptable alternate methods of highly effective contraception must be discussed in the event that the WOCBP participants chooses to forego complete abstinence

### NOTES:

a Typical use failure rates may differ from those when used consistently and correctly. Use should be consistent with local regulations regarding the use of contraceptive methods for participants participating in clinical studies.

b Hormonal contraception may be susceptible to interaction with the study drug, which may reduce the efficacy of the contraceptive method. Hormonal contraception is permissible only when there is sufficient evidence that the IMP and other study medications will not alter hormonal exposures such that contraception would be ineffective or result in increased exposures that could be potentially hazardous. In this case, alternative methods of contraception should be utilized.

c Intrauterine devices and intrauterine hormone releasing systems are acceptable methods of contraception in the absence of definitive drug interaction studies when hormone exposures from intrauterine devices do not alter contraception effectiveness

### Unacceptable Methods of Contraception\*

- Male or female condom with or without spermicide. Male and female condoms cannot be used simultaneously
- Diaphragm with spermicide
- Cervical cap with spermicide
- Vaginal Sponge with spermicide
- Progestogen-only oral hormonal contraception, where inhibition of ovulation is not the primary mechanism of action
- Periodic abstinence (calendar, symptothermal, post-ovulation methods)

- Withdrawal (coitus interruptus).
- Spermicide only
- Lactation amenorrhea method (LAM)

**\* Local laws and regulations may require use of alternative and/or additional contraception methods.**

## **CONTRACEPTION GUIDANCE FOR MALE PARTICIPANTS WITH PARTNER(S) OF CHILD BEARING POTENTIAL.**

Male participants with female partners of childbearing potential are eligible to participate if they agree to the following during the treatment and until the end of relevant systemic exposure.

- Inform any and all partner(s) of their participation in a clinical drug study and the need to comply with contraception instructions as directed by the investigator.
- Male participants are required to use a condom for study duration and until end of relevant systemic exposure defined as 7 months after the end of study treatment.
- Female partners of males participating in the study to consider use of effective methods of contraception until the end of relevant systemic exposure, defined as 7 months after the end of treatment in the male participant.
- Male participants with a pregnant or breastfeeding partner must agree to remain abstinent from penile vaginal intercourse or use a male condom during each episode of penile penetration during the treatment and until 7 months after the end of study treatment.
- Refrain from donating sperm for the duration of the study treatment and until 7 months after the end of study treatment.

## **COLLECTION OF PREGNANCY INFORMATION**

Guidance for collection of Pregnancy Information and outcome of pregnancy on the Pregnancy Surveillance Form is provided in [Section 9.2.5](#) and the [Appendix 3](#), Adverse Events and Serious Adverse Events: Definitions and Procedures for Evaluating, Follow-up and Reporting.

## **APPENDIX 5        MANAGEMENT ALGORITHMS**

These general guidelines constitute guidance to the Investigator and may be supplemented by discussions with the Medical Monitor representing the Sponsor. The guidance applies to all immuno-oncology agents and regimens.

A general principle is that differential diagnoses should be diligently evaluated according to standard medical practice. Non-inflammatory etiologies should be considered and appropriately treated.

[figure not shown]
Corticosteroids are a primary therapy for immuno-oncology drug-related adverse events. The oral equivalent of the recommended IV doses may be considered for ambulatory patients with low-grade toxicity. The lower bioavailability of oral corticosteroids should be taken into account when switching to the equivalent dose of oral corticosteroids.

Consultation with a medical or surgical specialist, especially prior to an invasive diagnostic or therapeutic procedure, is recommended.

The frequency and severity of the related adverse events covered by these algorithms will depend on the immuno-oncology agent or regimen being used.

## GI Adverse Event Management Algorithm

Rule out non-inflammatory causes. If non-inflammatory cause is identified, treat accordingly and continue I-O therapy. Opiates/narcotics may mask symptoms of perforation. Infliximab should not be used in cases of perforation or sepsis.

[figure not shown]

Patients on IV steroids may be switched to an equivalent dose of oral corticosteroids (e.g. prednisone) at start of tapering or earlier, once sustained clinical improvement is observed. Lower bioavailability of oral corticosteroids should be taken into account when switching to the equivalent dose of oral corticosteroids.

27-Jun-2019

## Renal Adverse Event Management Algorithm

Rule out non-inflammatory causes. If non-inflammatory cause, treat accordingly and continue I-O therapy.

[figure not shown]

Patients on IV steroids may be switched to an equivalent dose of oral corticosteroids (e.g. prednisone) at start of tapering or earlier, once sustained clinical improvement is observed. Lower bioavailability of oral corticosteroids should be taken into account when switching to the equivalent dose of oral corticosteroids.

27-Jun-2019

## Pulmonary Adverse Event Management Algorithm

Rule out non-inflammatory causes. If non-inflammatory cause, treat accordingly and continue I-O therapy. Evaluate with imaging and pulmonary consultation.

[figure not shown]

Patients on IV steroids may be switched to an equivalent dose of oral corticosteroids (e.g. prednisone) at start of tapering or earlier, once sustained clinical improvement is observed. Lower bioavailability of oral corticosteroids should be taken into account when switching to the equivalent dose of oral corticosteroids

27-Jun-2019

## Hepatic Adverse Event Management Algorithm

Rule out non-inflammatory causes. If non-inflammatory cause, treat accordingly and continue I-O therapy. Consider imaging for obstruction.

[figure not shown]
Patients on IV steroids may be switched to an equivalent dose of oral corticosteroids (e.g. prednisone) at start of tapering or earlier, once sustained clinical improvement is observed. Lower bioavailability of oral corticosteroids should be taken into account when switching to the equivalent dose of oral corticosteroids.

\*The recommended starting dose for grade 4 hepatitis is 2 mg/kg/day methylprednisolone IV.

27-Jun-2019

## Endocrinopathy Adverse Event Management Algorithm

Rule out non-inflammatory causes. If non-inflammatory cause, treat accordingly and continue I-O therapy. Consider visual field testing, endocrinology consultation, and imaging.

[figure not shown]

Patients on IV steroids may be switched to an equivalent dose of oral corticosteroids (e.g. prednisone) at start of tapering or earlier, once sustained clinical improvement is observed. Lower bioavailability of oral corticosteroids should be taken into account when switching to the equivalent dose of oral corticosteroids.

27-Jun-2019

## Skin Adverse Event Management Algorithm

Rule out non-inflammatory causes. If non-inflammatory cause, treat accordingly and continue I-O therapy.

Patients on IV steroids may be switched to an equivalent dose of oral corticosteroids (e.g. prednisone) at start of tapering or earlier, once sustained clinical improvement is observed. Lower bioavailability of oral corticosteroids should be taken into account when switching to the equivalent dose of oral corticosteroids.

[figure not shown]
\*Refer to NCI CTCAE v4 for term-specific grading criteria.

^If SJS/TEN is suspected, withhold I-O therapy and refer patient for specialized care for assessment and treatment. If SJS or TEN is diagnosed, permanently discontinue I-O therapy.

27-Jun-2019

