## 6.2 Exclusion Criteria

### 1) Medical Conditions

- a) Any active central nervous system (CNS) metastases
- b) Any prior AE that meets the criteria for treatment discontinuation as described in [Section 7.4.4](#), with the exception of patients with prior history of adrenal insufficiency that are under control with hormone replacement.
- c) Participants with treated CNS metastases for at least 1 month are eligible as long as they meet the following criteria:
  - i) Treated CNS metastases are defined as having no ongoing requirement for corticosteroids for at least 2 weeks (14 days) prior to first dose and no evidence of progression after treatment completed prior to first dose, as ascertained by clinical examination and brain imaging (magnetic resonance imaging [MRI] or CT). Stable dose of anticonvulsants is allowed. Treatment for CNS metastases may include whole brain radiotherapy, radiosurgery (eg, radiosurgery, gamma knife, linear accelerator, or equivalent) or a combination as deemed appropriate by the treating physician.
  - d) Participants with an active, known or suspected autoimmune disease. Participants with type I diabetes mellitus, hypothyroidism only requiring hormone replacement, skin disorders (such as vitiligo, psoriasis, or alopecia) not requiring systemic treatment, or conditions not expected to recur in the absence of an external trigger (eg, celiac disease) are permitted to enroll.
  - e) Participants with a condition requiring systemic treatment with either corticosteroids (> 10 mg daily prednisone equivalent) or other immunosuppressive medications within 14 days of first dose. Inhaled or topical steroids and adrenal replacement steroid doses > 10 mg daily prednisone equivalent are permitted in the absence of active autoimmune disease.
  - f) Uncontrolled adrenal insufficiency
  - g) Active infection requiring systemic therapy within 14 days prior to the first treatment dose
  - h) Not applicable per revised protocol 01.

- i) Participants with HIV infections are excluded if any of the following applies:
  - i) CD4+ T-cell count < 350 cells/ $\mu$ L
  - ii) Any AIDS-defining opportunistic infection occurred in the last 12 months
  - iii) HIV viral load is  $\geq$  400 copies/mL
  - iv) Antiretroviral therapy has been administered at current doses for less than 4 weeks
  - v) The participant is not on antiretroviral therapy
- j) Participants with a history of chronic hepatitis B or C are excluded if any of the following applies:

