### 7.4.2 Dose Delay Criteria

Nivolumab and ipilimumab administration should be delayed for the following:

- Grade 2 nonskin, drug-related AE, with the exception of fatigue
- Grade 2 drug-related creatinine, AST, ALT, and/or TBili abnormalities
- Grade 3 skin, drug-related AE
- Grade 3 drug-related laboratory abnormality, with the following exceptions:
  - Grade 3 lymphopenia or asymptomatic amylase or lipase does not require dose delay.
  - Grade  $\geq 3$  AST, ALT, and/or TBili will require dose discontinuation (see [Section 7.4.4](#)).
- Any AE, laboratory abnormality, or intercurrent illness that, in the judgment of the investigator, warrants delaying the dose of study medication

During Cycles 1 to 4, both nivolumab and ipilimumab must be delayed at the same time.

Participants who require delay of study treatment should be re-evaluated weekly or more frequently if clinically indicated and resume study treatment dosing when retreatment criteria are met. Tumor and other assessments should continue as per protocol even if dosing is delayed.

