#### **7.4.4.1 Nivolumab Dose Discontinuation**

Nivolumab treatment should be permanently discontinued for the following:

- Any Grade 2 drug-related uveitis, eye pain or blurred vision that does not respond to topical therapy and does not improve to Grade 1 severity within the retreatment period OR requires systemic treatment
- Any Grade 3 non-skin, drug-related AE lasting  $> 7$  days or recurs, with the following exceptions for laboratory abnormalities, neurologic toxicity, drug-related uveitis, pneumonitis, bronchospasm, hypersensitivity reactions, infusion reactions, and endocrinopathies:
  - Grade 3 drug-related neurologic toxicity, uveitis, pneumonitis, bronchospasm, myocarditis, hypersensitivity reaction, or infusion reaction of any duration requires discontinuation
  - Grade 3 drug-related endocrinopathies, adequately controlled with only physiologic hormone replacement do not require discontinuation. Adrenal insufficiency requires discontinuation regardless of control with hormone replacement.
  - Grade 3 drug-related laboratory abnormalities do not require treatment discontinuation except:
    - ◆ Grade 3 drug-related thrombocytopenia  $> 7$  days or associated with bleeding requires discontinuation
    - ◆ Grade  $\geq 3$  drug-related AST, ALT, or TBili requires discontinuation\*
    - ◆ Concurrent AST or ALT  $> 3 \times$  ULN and TBili  $> 2 \times$  ULN
- \*In most cases of Grade 3 AST or ALT elevation, study treatment will be permanently discontinued. If the investigator determines a possible favorable benefit/risk ratio that warrants continuation of study treatment, a discussion between the investigator and the BMS medical monitor/designee must occur.
- Any Grade 4 drug-related AE or laboratory abnormality (including but not limited to creatinine, AST, ALT, or TBili), except for the following events, which do not require discontinuation:
  - Grade 4 neutropenia  $\leq 7$  days
  - Grade 4 lymphopenia or leukopenia or asymptomatic amylase or lipase
  - Isolated Grade 4 electrolyte imbalances/abnormalities that are not associated with clinical sequelae and are corrected with supplementation/appropriate management within 72 hours of their onset

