### **10.3.2 Safety Analyses**

All safety analyses for nivolumab will be performed on the Safety Sample.

Endpoint	Statistical Analysis Methods
Secondary	
The safety analysis will be performed in all treated participants. Descriptive statistics of safety will be presented using the NCI CTCAE version 5.0 by treatment arm. All AEs, drug-related AEs, SAEs, and drug-related SAEs will be tabulated using the worst grade per NCI CTCAE version 5.0 criteria by system organ class and preferred term. On-study laboratory parameters including hematology, chemistry, liver function, and renal function will be summarized using worst grade per NCI CCAE version 5.0 criteria.
 
AE incident rate is defined as the proportion of participants with any grade AEs among treated participants. Events reported from the first dose and up to and including 100 days following the last dose of study treatment could be included in estimating this incidence rate.

Abbreviations: AE = adverse event; NCI CTCAE = National Cancer Institute Common Terminology Criteria for Adverse Events; SAE = serious adverse event

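### For SJS/TEN below Grade 4, Appendix 5 stops treatment permanently while Sections 7.4.2 to 7.4.4 allow delay and restart, and exclusion 1b does not expressly cover a prior, resolved case

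*Combined protocol and SAP*

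**What the plan says.** **Appendix 5, skin algorithm.** For a suspected case: "If SJS/TEN is suspected, withhold I-O therapy and refer patient for specialized care for assessment and treatment". For a diagnosed case: "If SJS or TEN is diagnosed, permanently discontinue I-O therapy". Neither sentence carries a grade. The introduction to Appendix 5 describes its own standing: "These general guidelines constitute guidance to the Investigator and may be supplemented by discussions with the Medical Monitor representing the Sponsor".

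**Section 7.4.2.** The list of reasons to delay both drugs includes "Grade 3 skin, drug-related AE".

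**Section 7.4.3.** Dosing may restart once a drug-related event is back to Grade 1 or less, or to baseline. The one skin exception concerns restarting while Grade 2 skin toxicity persists. SJS/TEN is not mentioned.

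**Sections 7.4.4.1 and 7.4.4.2.** The Grade 3 stop rule for each drug opens "Any Grade 3 non-skin, drug-related AE lasting" more than 7 days. Both lists go on to name particular Grade 3 events that stop treatment whatever their duration, and SJS/TEN is not among them. Both lists stop treatment for any Grade 4 drug-related event, with a few exceptions, none of them a skin event.

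**Section 8.1.** The list of mandatory reasons to stop cites Section 7.4.4 and does not cite Appendix 5.

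**Section 6.2, exclusion 1b.** It bars "Any prior AE that meets the criteria for treatment discontinuation as described in" Section 7.4.4, with a carve-out only for controlled adrenal insufficiency. Section 5.1 uses the same reference.

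**The concern.** A site that reads Section 7.4 and a site that reads Appendix 5 could each believe it is following the protocol and still act in opposite ways on the same diagnosis. One would end treatment; the other would hold it and restart.

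The design adds a second consequence. Everyone enrolled has already received both drugs, and exclusion 1b is the criterion that keeps out people who had a treatment-stopping reaction to them. Because it takes its content from Section 7.4.4 alone, whatever that section leaves out is also left out at entry.

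**Working it through.** No error rate, sample size or event count is involved, so the check sets the passages side by side by grade.

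1. **Grade 4, drug-related.** Sections 7.4.4.1 and 7.4.4.2 stop treatment. Their exceptions cover certain blood counts, amylase or lipase, electrolytes and endocrine events, and no skin event. Appendix 5 also stops treatment. A prior case meets Section 7.4.4 and is barred by exclusion 1b. The texts agree.

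2. **Grade 3, on study.** Section 7.4.2 gives a delay. Section 7.4.3 permits restart at Grade 1 or less, or baseline, and says delayed doses should be given as soon as those conditions are met. The Grade 3 stop rules do not apply, because they are confined to non-skin events. Appendix 5 gives a permanent stop. The texts contradict each other.

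3. **Below Grade 3, on study.** The Grade 2 entries in Section 7.4.2 leave skin events out, and the only Grade 2 stop in Section 7.4.4 concerns the eye. Appendix 5 would still stop treatment. The documents do not say whether SJS or TEN can be graded this low, so this category may be empty.

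4. **Precedence.** Section 7.4 lists skin among the Appendix 5 groups and applies the algorithms and the delay, resume and stop criteria to both drugs. It calls the algorithms recommended and does not say which text governs when they differ. Appendix 5 calls itself guidance, and Section 8.1 makes only Section 7.4.4 mandatory.

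5. **Prior case, resolved, below Grade 4.** Exclusion 1b leads to Section 7.4.4, where no listed criterion is met (steps 2 and 3). Exclusion 1n covers only toxicity that has not resolved. What remains is investigator judgment: the substantial-risk clauses that close Sections 7.4.4.1 and 7.4.4.2, and exclusion 1o.

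6. **Grading version.** The skin algorithm's footnote reads "Refer to NCI CTCAE v4 for term-specific grading criteria". Section 10.3.2 reads "Descriptive statistics of safety will be presented using the NCI CTCAE version 5.0", and exclusion 1n and Section 7.4.5 also use version 5.0. The outcome in steps 1 to 3 turns on grade, so the version should be the same throughout.

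**The case against.** The strongest reply is that the texts can be obeyed together. Section 7.4 brings the algorithms in. The SJS/TEN sentence is specific and imperative, while Section 7.4.3 is general and mostly permissive, so a site that never restarts breaches neither. Calling Appendix 5 guidance that may be supplemented is not the same as saying it may be overridden. This has force and is probably how a careful site would read it. But it depends on a rule of precedence that the protocol does not state, and Section 7.4.3 also urges prompt dosing once its conditions are met.

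Other provisions narrow the entry gap:
- The judgment clauses sit inside Section 7.4.4, so exclusion 1b arguably carries them.
- Exclusion 1o bars anyone whose condition raises the risk of study drug, in the investigator's opinion.
- Exclusion 4b covers severe hypersensitivity to a monoclonal antibody, but the text does not say whether SJS/TEN counts.
- Inclusion 2c requires progression on nivolumab maintenance, and someone taken off first-line treatment for SJS/TEN would ordinarily not meet it.

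Each is discretionary or indirect. They reduce the chance of entry without supplying an express rule.

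Three stronger readings are tempting, and the documents do not support them:
- A reader might infer that any prior or on-study SJS/TEN could be re-exposed. Grade 4 cases cannot be under either text.
- A reader might take the Grade 3-4 skin rate in Table 3.2.6.4-2, 20/547 = 3.7%, multiply by 96 and conclude that about 3.5 participants fall under conflicting rules. That rate counts all drug-related Grade 3-4 skin events. The conflict shown here concerns SJS/TEN below Grade 4 only, and 96 is a target for enrolled rather than treated participants.
- A reader might infer that the two CTCAE versions would assign different grades. Nothing in the documents shows this for any skin event.

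**Conclusion.** The contradiction is real and confined to drug-related SJS/TEN below Grade 4: Appendix 5 ends treatment, and Sections 7.4.2 to 7.4.4 delay it and allow restart. The matching gap at entry is that a prior, resolved case of that kind is not expressly excluded and is left to investigator judgment.

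The size cannot be given, because the documents state neither how often SJS/TEN occurs on this regimen, nor how it is graded, nor what share falls below Grade 4. The case for acting rests on the consequence for a participant and on the retreatment design, not on frequency.

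Two conditions apply. The figure in the skin algorithm is not available in the text reviewed and may hold further rules, although the footnote on SJS/TEN is complete without it. The conclusion also assumes that no statement of precedence exists elsewhere; none was found in Sections 5.1, 7.4 or 8.1 or in the introduction to Appendix 5. The CTCAE mismatch is a minor, secondary point.

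**What to change.** - Reconcile Sections 7.4.2, 7.4.3, 7.4.4.1, 7.4.4.2 and Appendix 5 so that they give one instruction for suspected and one for diagnosed SJS/TEN.
- Make exclusion 1b and Section 5.1 refer to the reconciled criteria, and state whether prior SJS/TEN is covered.
- As a tidy-up, reconcile the CTCAE version in the skin algorithm with the version used in the rest of the protocol.

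Which rule stands is for the sponsor's medical team. The cost is wording in the next amendment, with no new procedure, visit or participant.
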